Appendix 10 – Discussion guide

Introduction

Name: Introduce PA representative

Duration of review meeting: 60 minutes

Note to moderator: Warn participants that the computer will say "This session is now being recorded" when press record [allow pause for this]

PRESS RECORD IN VALIDATELY

Moderator: Welcome and thank you for agreeing to take part in this study. My name is ______ and I am an independent researcher.

I would just like to check that you have read the Informed Consent/assent you agree to what it says, and have signed the form. **[pause for answer].** Do you have any questions about the form?

I will be asking a you to undertake a Covid-19 virus test and I will be asking a few questions about your experience doing this.

I do have a colleague and representatives from our client observing the session remotely.

The study that we are running today is a regulatory study which we are conducting on behalf of the government before this test kit is allowed to be released to the public. We therefore ask that you take this session very seriously as your contribution today has a direct impact on the release of this test kit to the wider public.

Remind:

- If you have a mobile phone, please would you mind turning it on silent for the session?
- The session will last about between 60 minutes.
 - The session is being video recorded by the cameras in Validately
 - The session will be viewed remotely by members of the research team.
- The material you will be using today is Confidential, and the document you have signed is a Confidentiality Agreement, so please don't talk to anyone else about what you see today.
- We will be keeping any sensitive information you provide to us confidential, as outlined in the consent form.
- You can withdraw from the session at any time and without penalty; you do not have to give a reason.

I am now going to get you to unpack the supply of items you will need for today.

Please can you open the envelope labelled 'Do not open until instructed' and take out the contents.

...BUT PLEASE DON'T OPEN THE TEST KIT (which is contained within the clear bag). INSIDE UNTIL I TELL YOU TO

In your envelope there should also be:

- Hand gel
- Participant ID label
- Stamp addressed envelope for return of the webcam
- IFU
- Spare swab

Note to moderator: Check you can see whole of the assessment area with the participant positioned as if they were about to start doing the simulated use.

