4.4 Simulated use adult and adolescents

Participants will be asked to open the pack and to follow the steps of use presented to them.

The moderator will observe the participant complete the steps of use. To ensure the task is representative of a real-use scenario, the moderator will not interact with the participant during this task and will not offer help to the participant. The moderator will only verbally interject if the participant gives up on the task, or if the moderator foresees a dangerous scenario developing. A list of tasks and their success/use-error criteria are found in the discussion guide Appendix 6 and section 4.1.1

During the simulated use participants are expected to undertake all steps as described in the IFU to perform a self-test using the LFD test kit.

This task begins with all the study components in their unopened form on the table and ends with the participant indicating that they have done everything they would do at home to perform the test.

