6.3 ADULT/ADOLESCENT Simulated use and Root Cause (40 mins)

NOTE TO MODERATOR – GO TO NEXT SECTION IF CAREGIVER

The test-kit that you are going to use today is detects the presence of COVID-19. You would use this test-kit on yourself or someone you care for, and it would be posted to your home as part of the UK Government's Test and Trace scheme.

I now want you to imagine that you have been sent the test kit and it's time to perform the test on yourself. Remember this is a real test which is going to give you a real result, so please do everything you would do if I weren't here today. Once you have finished let me know and I will ask you some questions.

When giving yourself the test, please refer to the instructions provided to you in the kit.

Do you have any questions before we start?

You may now proceed to do the test.

REFERRED TO IFU? YES / NO

Use Step/Acceptance criteria	Use Error	Use Difficulty	Close Call	Pass	Comments	
Clear, clean and dry a flat surface to place the home test kit on.						
Wash your hands thoroughly for 20 seconds, using soap and warm water, or hand sanitiser.						
Take the test kit out of the foil packaging and place it onto the cleaned flat surface.						
Setup your test						
Use Step 1 Carefully twist or snap open the sachet						

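### The opening script asks participants to be especially serious because the session affects release; this works against representative use and may understate use errors by an unknown amount

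*Protocol*

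**What the plan says.** The objective (Protocol, section 2.2) is to validate safe and effective use by the intended users in the intended environment, which section 2.8 describes as primarily the home. Section 4.4 turns that into a rule of conduct: "To ensure the task is representative of a real-use scenario, the moderator will not interact with the participant during this task". Help is also ruled out, except where the participant gives up or danger is foreseen.

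The introduction in Appendix 10 comes before the split into the self-test script (6.3) and the caregiver script (6.4), so participants in all four user groups hear it. It tells them that "I do have a colleague and representatives from our client observing the session remotely", and then that "The study that we are running today is a regulatory study which we are conducting on behalf of the government". The next sentence asks them to "take this session very seriously as your contribution today has a direct impact on the release of this test kit".

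After the background questions in 6.1 and 6.2, scripts 6.3 and 6.4 tell the participant that the test and its result are genuine and add "please do everything you would do if I weren't here today". Both then ask the participant to refer to the instructions in the kit.

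**The concern.** What the study needs to observe is how people perform with the kit and its instructions for use (IFU) when nobody has given them an extra reason to be careful. The protocol controls the moderator's influence during the task but scripts some of it shortly beforehand. A person opening the kit at home is not told that the release of a product partly depends on them.

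If the request raises care, errors that would occur at home are less likely to appear in the session. An error that does not appear gets no root-cause investigation and prompts no change to the IFU. Because every participant hears the same introduction, there is no unprimed group from which the analysis could estimate or remove the effect.

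**Working it through.** **Who is exposed.** Table 4 gives four groups of 15: 4 × 15 = 60, which agrees with the stated total. The introduction is common to all of them, so all 60 are exposed before the first scored step.

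**Order of messages.** (1) Appendix 10 introduction: regulatory context, then the request to be very serious. (2) Sections 6.1 and 6.2, scheduled at 5 + 2 = 7 minutes. (3) Section 6.3 or 6.4: act as if the moderator were absent, and use the instructions. (4) Scored use. The counter-instruction is therefore the later message, but it does not withdraw the earlier one. Nowhere in the script are participants told that the kit, and not they, is being assessed.

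**Which outcomes could move.**
- Simulated-use steps (Table 7) are the most exposed. Several criteria reward diligence more than comprehension: cleaning and drying the surface, washing hands a second time, ten full circles in the nostril, 15 seconds of pressing and rotating the swab.
- Knowledge questions (sections 4.6 and 6.6) are little exposed, because participants are already told to consult the materials when answering.
- Close calls and use difficulties (Table 10) could move either way, because re-reading a part of the IFU counts under both definitions. A more careful participant may re-read more.

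**Size.** The protocol gives no expected error rate, no acceptable error rate and no estimate of an observation effect, so the bias cannot be computed. The following only shows what assumed reductions would do. With n participants and error probability p on a step, independent between participants,

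P(at least one error) = 1 − (1 − p)^n.

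| Assumed home error rate | Reduction through the request | Rate in session | n = 15 | n = 60 |
|---|---|---|---|---|
| 5% | none | 5% | 53.7% | 95.4% |
| 5% | a quarter | 3.75% | 43.6% | 89.9% |
| 5% | a half | 2.5% | 31.6% | 78.1% |
| 10% | none | 10% | 79.4% | 99.8% |
| 10% | a quarter | 7.5% | 68.9% | 99.1% |
| 10% | a half | 5% | 53.7% | 95.4% |
| 20% | none | 20% | 96.5% | above 99.8% |
| 20% | a quarter | 15% | 91.3% | above 99.8% |
| 20% | a half | 10% | 79.4% | 99.8% |

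For example, 1 − 0.90^15 = 0.794 and 1 − 0.95^15 = 0.537. In expected counts over all 60, a 10% rate that is halved goes from 60 × 0.10 = 6 errors to 60 × 0.05 = 3. Across all 60, an error with a home rate of 10% or more would still almost certainly be seen at least once under these assumptions. The loss falls mainly on rarer errors and on findings within a single user group.

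**The case against.** The strongest reply is that the effect is unproven and its direction open. The script asks and does not command, and it speaks of the participant's contribution, not performance; a participant could take that as an invitation to report problems honestly. The last framing before the task is to behave as at home. Participants are paid £50 and did not seek the test, so they may be less engaged than a real user, and a request for seriousness could restore some of that. The IFU itself contains motivating text that home users also see. Being watched can cause errors as well as prevent them. Video recording, the client observers and the prompt to use the instructions would all remain after any rewording.

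Most of this stands, and it limits the claim. A reader might infer that every step and every question is shifted towards fewer errors. The documents do not support that: re-reading is itself scored adversely, and the knowledge questions are open-book by design. A reader might also infer that the root-cause interview is compromised because participants will hide difficulties. That is conjecture: 6.5 probes difficulties that were observed, and section 4.11 draws on video and expert review as well as on what participants report.

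What the reply does not do is justify the sentence. Engagement is already secured in 6.3 and 6.4, which stress that the test and its result are genuine. That motive is one a home user shares; responsibility for a release decision is not.

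**Conclusion.** The point holds as a risk, not as a demonstrated bias. The request to be very serious, tied to release of the kit, conflicts with the protocol's own aim of representative use, reaches all 60 participants before any scoring, and is softened but not cancelled by the later instruction. The most plausible consequence is some understatement of use errors on the diligence-dependent simulated-use steps. This rests on the assumption that the request raises care for at least some participants, which the protocol neither shows nor excludes.

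The size is unknown; the table under the check is illustration only. The protocol states no pass threshold, so no stated decision can be shown to change, and no sample-size figure depends on the point. It is still worth correcting, because the source of bias is avoidable and the remedy is one sentence.

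**What to change.** In the Appendix 10 introduction, delete the sentence that begins with the request to take the session very seriously. Put a neutral one in its place, for example: *we are assessing the kit and its instructions, not you; please act as you would at home.*

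Keep a plain factual statement that the kit is being evaluated before release. A reader might conclude that all mention of the regulatory purpose should move to the debrief. That is unnecessary and would withhold context from people before they take part; the bias concern lies in the appeal, not in the disclosure.

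If sessions have already run with the present script, record in the study report that participants were given this message, that it may have reduced observed use errors, and that the size of any reduction cannot be estimated.

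The cost is one sentence of script, with no effect on sample size or timetable. Success rates may come out slightly less favourable. Participants lose one prompt to engage, which the wording in 6.3 and 6.4 about a genuine test and result already supplies.

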6.1 Introductory questions / screener confirmation (5 mins)

Today we are going to ask you to administer a Covid-19 test using the materials provided to you, and then ask you some follow up questions on your experience.

First, I would like to ask you some background questions about yourself and any experience you may have using an in-home test kit

1.	Are you right or left-handed?	
2.	How old are you?	
3.	Do you wear glasses/contacts to read? [Ensure they have brought their glasses with them]	
4.	Are you colour blind or colour deficient?	
5.	Do you have trouble gripping and holding objects?	

6.2 Baseline patient experiences (2 mins)

 Have you taken a home test before for anything? Probe: What was the test for? Probe: What was your experience when taking the test? Probe: How easy was the test to perform? Probe: Did you have any difficulty following the instructions?

6.3 ADULT/ADOLESCENT Simulated use and Root Cause (40 mins)

NOTE TO MODERATOR – GO TO NEXT SECTION IF CAREGIVER

The test-kit that you are going to use today is detects the presence of COVID-19. You would use this test-kit on yourself or someone you care for, and it would be posted to your home as part of the UK Government's Test and Trace scheme.

I now want you to imagine that you have been sent the test kit and it's time to perform the test on yourself. Remember this is a real test which is going to give you a real result, so please do everything you would do if I weren't here today. Once you have finished let me know and I will ask you some questions.

When giving yourself the test, please refer to the instructions provided to you in the kit.

Do you have any questions before we start?

You may now proceed to do the test.

REFERRED TO IFU? YES / NO

Use Step/Acceptance criteria	Use Error	Use Difficulty	Close Call	Pass	Comments	
Clear, clean and dry a flat surface to place the home test kit on.						
Wash your hands thoroughly for 20 seconds, using soap and warm water, or hand sanitiser.						
Take the test kit out of the foil packaging and place it onto the cleaned flat surface.						
Setup your test						
Use Step 1 Carefully twist or snap open the sachet						

6.3.1 LFD TEST ADULT OR ADOLESCENT SELF TEST

Use Step/Acceptance criteria	Use Error	Use Difficulty	Close Call	Pass	Comments
Use Step 2					
Pour all of the fluid from the sachet into the extraction tube.					
Use Step 3 Place the filled tube in a cup or container to avoid spilling it while you use the swab					
Use Step 4 Check the swab in the sealed wrapper in front of you					
Use step 5 Gently blow your nose into a tissue.					
Use step 6 Wash and dry your hands again (or use sanitiser if this is available).					
Use Step 7 Open the swab package and gently take out the swab.					
Take your swab sample					
Use step 8 Holding the swab between your fingers, open your mouth wide and rub the fabric tip of the swab over both tonsils (or where they would have been). Do this with firm contact 4 times on each side (use a mirror to help you do this). Carefully remove the swab from the back of your throat.					

Use Step/Acceptance criteria	Use Error	Use Difficulty	Close Call	Pass	Comments
Use step 9					
Put the same swab gently into one nostril until you feel a slight resistance (about 2.5cm up your nose).					
Roll the swab firmly around the inside of the nostril, making 10 complete circles.					
Process the swab sample					
Use step 10					
Remove the extraction tube from the cup and place the fabric tip of the swab into the extraction tube so it is in the fluid.					
Press the tip against the edge of the extraction tube with force, while rotating it around the tube for 15 seconds.					
Use step 11					
Pinch the tube as you remove the swab to make sure that all the fluid is removed from the soft tip of the swab.					
Place the swab in the plastic waste bag provided.					
Use step 12					
Press the nozzle cap tightly on to the extraction tube to avoid any leaks					
Use step 13					
Gently squeeze the extraction tube to place 2 drops of liquid onto the specimen well on the test strip.					

Use Step/Acceptance criteria	Use Error	Use Difficulty	Close Call	Pass	Comments
Use step 14 Place the test strip on a flat and level surface Check the time or set a timer if you have one. Wait 30 minutes to read your result.					

START TIMER (30 minutes)

NOTE TO MODERATOR: AFTER STEP 14 ASK THE PARTICIPANT HOW LONG THEY SHOULD WAIT TO READ THE RESULTS

Wait full 30 minutes before reading results. A positive result can appear at any time after 20 minutes, however you must wait for a full 30 minutes to record a negative result as the test line may take longer to appear.

WHILE WAITING FOR THE TEST RESULTS PROCEED WITH 6.5

NOTE TO MODERATOR: RECORD CURRENT TIME AND SET A TIMER FOR 30 MINUTES.

6.4 **CAREGIVER** Simulated use and Root Cause (40 mins)

The test-kit that you are going to use today is detects the presence of COVID-19. You would use this test-kit on yourself or someone you care for, and it would be posted to your home as part of the UK Government's Test and Trace scheme.

I now want you to imagine that you have been sent the test kit and it's time to perform the test on your child/family member. Remember this is a real test which is going to give you a real result, so please do everything you would do if I weren't here today. Once you have finished let me know and I will ask you some questions.

When giving yourself the test, please refer to the instructions provided to you in the kit.

Do you have any questions before we start?

You may now proceed to do the test.

REFERRED TO IFU? YES / NO

Use Step/Acceptance criteria	Use Error	Use Difficulty	Close Call	Pass	Comments
Clear, clean and dry a flat surface to place the home test kit on.					
Wash your hands thoroughly for 20 seconds, using soap and warm water, or hand sanitiser.					
Take the test kit out of the foil packaging and place it onto the cleaned flat surface.					
Setup your test					
Use Step 1 Carefully twist or snap open the sachet					
Use Step 2 Pour all of the fluid from the sachet into the extraction tube.					

Use Step/Acceptance criteria	Use Error	Use Difficulty	Close Call	Pass	Comments
Use Step 3 Place the filled tube in a cup or container to avoid spilling it while you use the swab					
Use Step 4 Check the swab in the sealed wrapper in front of you					
Use step 5 (Not required for non self test) Gently blow your nose into a tissue.					
Use step 6 Wash and dry your hands again (or use sanitiser if this is available).					
Use Step 7 Open the swab package and gently take out the swab.					
Take your swab sample					
Use step 8 (child/dependant) Ask the child to open their mouth wide, then rub the fabric tip of the swab over both tonsils (or where they would have been). Do this with firm contact 4 times on each side. Carefully remove the swab. If you cannot swab the tonsils, you can swab both nostrils.					

Use Step/Acceptance criteria	Use Error	Use Difficulty	Close Call	Pass	Comments
Use Step 9 (child/dependent)					
Put the fabric tip of the same swab gently into one of their nostrils until you feel some resistance.					
Roll the swab firmly around the inside of the nostril, making 10 complete circles and slowly remove it. If you could not swab their throat repeat in their other nostril.					
Process the swab sample					
Use step 10					
Remove the extraction tube from the cup and place the fabric tip of the swab into the extraction tube so it is in the fluid.					
Press the tip against the edge of the extraction tube with force, while rotating it around the tube for 15 seconds.					
Use step 11					
Pinch the tube as you remove the swab to make sure that all the fluid is removed from the soft tip of the swab.					
Place the swab in the plastic waste bag provided.					
Use step 12					
Press the nozzle cap tightly on to the extraction tube to avoid any leaks					

Use Step/Acceptance criteria	Use Error	Use Difficulty	Close Call	Pass	Comments
Use step 13 Gently squeeze the extraction tube to place 2 drops of liquid onto the specimen well on the test strip.					
Use step 14 Place the test strip here (Optional). Check the time or set a timer if you have one. Wait 30 minutes to read your result.					

START TIMER (30 minutes)

NOTE TO MODERATOR: AFTER STEP 14 ASK THE PARTICIPANT HOW LONG THEY SHOULD WAIT TO READ THE RESULTS

Wait full 30 minutes before reading results. A positive result can appear at any time after 20 minutes, however you must wait for a full 30 minutes to record a negative result as the test line may take longer to appear.

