3.6 Participants

The total sample size for this study will be 60 participants administering the test. There will be 4 user groups. A breakdown of composition of each group is detailed Table 4.

Table 4 - Study sample

User groups	Sample size
Adolescents between the age of 12 and 17	15
Adults aged 18+	15
Adults administering the test to an adult dependant	15 caregivers plus 15 dependants
Adults administering the test to a child under the age of 12	15 parents plus 15 children

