4.5 Simulated use caregivers of paediatrics and dependents

Participants will be asked to open the pack and to follow the steps of use presented to them to perform the test on their child/ dependent.

The simulated use steps to be observed are as follows in table 8:

Table 8 - Use	Steps for	adult testing	a child	or dependent

Use Step	Acceptance criteria
Repeat Use Steps 1 through 7 as per Section 4.4.1 (table 7) of this protocol, then proceed with Use Steps 8 and 9 below.	As per section 4.4.1 (table 7)
Use step 8 (child/dependant) Ask the child to open their mouth wide, then rub the fabric tip of the swab over both tonsils (or where they would have been). Do this with firm contact 4 times on each side. Carefully remove the swab. If you cannot swab the tonsils, you can swab both nostrils.	Participant rubs the fabric tip of the swab over both tonsils with firm contact 4 times on each side, without touching any part of the child/ dependent's mouth at this stage (not touching tongue, teeth, cheeks, gums etc). Participant removes the swab from the child/dependent's throat without touching any part of their mouth at this stage (not touching tongue, teeth, cheeks, gums etc)
Use Step 9 (child/dependent) Put the fabric tip of the same swab gently into one of their	Participant puts the fabric tip of the same swab gently into one of their nostrils Participant rolls the swab firmly
nostrils until you feel some resistance. Roll the swab firmly around the inside of the nostril, making 10 complete circles and slowly remove it. If you could not swab	around the inside of the nostril, making 10 complete circles and slowly removes it.
their throat repeat in their other nostril.	If the user could not swab the throat, they repeat in the other nostril.
Repeat Use Steps 10 through 14 , as per Section 4.4.1 (table 7) of this protocol.	As per section 4.4.1 (table 7)

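### The caregiver script in section 6.4 tells caregivers they are giving the test to themselves, directly after assigning them to test someone else

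*Protocol*

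**What the plan says.** Section 4.5 of the protocol asks caregivers to open the pack and "follow the steps of use presented to them to perform the test on their child/ dependent". Table 8 gives them their own Steps 8 and 9, performed on the child or dependant.

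The caregiver script is section 6.4 of the discussion guide (Appendix 10). It asks the caregiver to imagine that the kit has arrived and that "it's time to perform the test on your child/family member". The next paragraph reads: "When giving yourself the test, please refer to the instructions provided to you in the kit". The moderator then invites questions and starts the task.

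The same sentence stands word for word in section 6.3, the self-test script for adults and adolescents.

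On numbers, section 3.6 says: "The total sample size for this study will be 60 participants administering the test". Table 4 lists the two caregiver groups as "15 caregivers plus 15 dependants" and "15 parents plus 15 children".

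**The concern.** The script gives caregivers two incompatible statements about who is to be tested, and the wrong one comes second. It is the last substantive instruction before the start, and it is the sentence that sends the participant to the IFU, which is what the study evaluates.

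The study scores how well people follow instructions, and its threshold for recording a problem is low. Under Table 10, re-reading one part of the IFU to work out the sequence appears under both Close Call and Use Difficulty. A caregiver who pauses to check whether the self-test instructions apply could therefore be scored for confusion that the moderator introduced. One who actually began a self-test would fail the task set in 4.5. In either case the record would count against the IFU something the IFU did not cause.

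**Working it through.** **1. Who hears the line.** Inputs are from Table 4.

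- All groups: 15 + 15 + 15 + 15 = 60, which reproduces the stated total.
- Caregivers: 15 (adult dependants) + 15 (children) = 30.
- Share of those administering the test: 30/60 = 50%.

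**2. The texts side by side.**

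| Place | Who is to be tested |
|---|---|
| Section 6.3, assignment | the participant |
| Section 6.3, IFU sentence | the participant (consistent) |
| Section 4.5 and Table 8 | the child or dependant |
| Section 6.4, assignment | the child or family member |
| Section 6.4, IFU sentence | the participant (contradicts the three lines of text above it that concern caregivers) |

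The two IFU sentences are identical, so the likeliest explanation is that the line was carried from 6.3 to 6.4 without adaptation.

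**3. How a resulting event would be scored.** These definitions are in Table 10.

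- Hesitation with re-reading: Close Call or Use Difficulty.
- Self-testing: it does not meet the task in 4.5, so Use Error.
- Exclusions: the only listed exclusion from Use Error is a packaging malfunction. N/A applies only when a task cannot be completed for a reason outside the participant's control.

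A problem prompted by the script therefore has no clear category of its own. Root cause questioning follows each problem, but the prompt in section 6.5 asks about difficulties in general and not about the moderator's wording.

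**4. Would using the self-test steps on the child fail Table 8?** Not necessarily.

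- Step 8: both sets of instructions call for four firm rubs on each tonsil.
- Step 9: both require ten circles in a nostril with the same swab. Table 7 adds the second nostril. Table 8 requires it only if the throat could not be swabbed, and states no criterion that fails a caregiver who swabs both.

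Only testing the wrong person would clearly fail.

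**5. Size per affected session.**

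- Within one caregiver group: 1/15 = 6.7 percentage points on a step's proportion.
- Across both caregiver groups: 1/30 = 3.3 percentage points.
- Number of sessions affected: anywhere from 0 to 30. The documents give no rate.

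**The case against.** The strongest reply is that hardly anyone would be misled.

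- The explicit assignment comes immediately before the line.
- Caregivers are recruited for this task, are asked in the screener whether they are willing to test the child or dependant, and attend with that person.
- Table 3 makes the moderator responsible for seeing that the spoken task is understood.
- Questions are invited after the line and before the start.
- Section 4.11 requires root cause analysis of every use problem from video, interviews and expert review, so a cause in the script could be found.

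All of this stands, and it makes the likely effect small. It does not remove the contradiction. These safeguards depend on the participant or the moderator noticing it.

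A reader might also infer more than the documents support:

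- *That the line sends caregivers to the wrong part of the IFU.* It names no page or section, only the kit's instructions as a whole. The IFU's swabbing pages cannot be seen in the available text, and a heading in Table 7 that covers the user's own sample or the child's suggests a shared section.
- *That the moderator could not correct a mistake.* The rule against interacting is in section 4.4, for adults and adolescents, and is not restated in 4.5. Even in 4.4 the moderator may step in if the participant gives up or danger is foreseen.

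**Conclusion.** The contradiction is certain: the wording is in the operative script, it is read to 30 of the 60 people administering the test, and it conflicts with the script's own assignment, section 4.5 and Table 8. Its effect is only a possibility. It could prompt hesitation or re-reading and, less plausibly, self-testing, any of which would be scored as a use problem not caused by the IFU.

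It would be tempting to conclude that the line induces errors, or that the results of two of the four groups are contaminated. The documents show neither. They report no such error and give no rate from which to estimate one, and the count of 30 measures exposure, not effect. The protocol also states no numerical pass threshold, so the 6.7 points per affected session show scale but are tied to no decision rule.

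This is a minor wording error. It is worth correcting because it is spoken to participants just before a scored task. The conclusion assumes that moderators read the script as written.

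**What to change.** - In section 6.4, replace the reference to giving oneself the test with wording that matches the assignment, for example: *When giving the test to your child or the person you care for*. The rest of the sentence can stand.
- Leave section 6.3 unchanged.
- For any session run with the current wording of 6.4, record a use problem traced to it as script-induced in the root cause analysis. The session videos allow a check of what the moderator actually said.

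The cost is one phrase in the discussion guide and one instruction to moderators and observers. No sample size, step, acceptance criterion or clinical rule changes.
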